**REVISION HISTORY**

Revision #	Version Date	Summary of Changes	Consent Change?
2	2/10/2020	Removing language of HIPAA waiver. Information sheets updated to include HIPAA and data use language.	Y

PROTOCOL TITLE: Education about Health and Cancer Study

3	3/17/2020	
Consent Changes:
 
For Experimental Arm 2 and Control Arm (both online: Adding language to Information sheets to include information about participant ability to download e-signed consent form.
 
For Experimental Arm 1: Adding HIPAA language to consent script (which should have been done during our 2/10/2020 modification) and adding a signature line to information sheet since we are able to collect actual written signatures from those participants.
 
For All Arms: Adding privacy/confidentiality risk language and request for personal information and that data will be stored for 6 years No longer requesting waiver of signature
	Y
---	-----------	---	---

PROTOCOL TITLE: Education about Health and Cancer Study

		
(except that Experimental Arm 2 and Control are e-signatures).
 
See information sheets, script, and protocol section 18 for changes.
 
Other Changes:      Changing length of time data is stored (6 years).
 
Adding the six control arm dummy questions to all arms of study (not just control arm).
 
Clarifying identifying information to be included in Experimental Arm 2 and Control Arm (to match Experimental Arm 1 information)
 
Clarifying that all participants who pre-screen as eligible for both identified PI studies and DCC clinical trials and agree to have contact information shared will be referred (not just Experimental Arm 1 participants)
 
Modifying online format for Experimental Arm 2 from just a video to an online module to include a video plus written education.
 
Updating recruitment verbiage to reflect the video plus written education.
 
Adding documents for review:      -Video script      -Referrals data tracking sheets (referrals to research nurses and research teams/PIs for possible enrollment in studies)
	
4	6/12/2020	
Consent Form changes, including initials; see tracked changes on consent forms
 
Other revisions within protocol:      -Clarifying sample size for Exp. Arm 2 and Control Arm.      -Modified recruitment plans for Exp Arm 2 and Control Arm (unpaid social media posts)
	Yes

## PROTOCOL TITLE: Education about Health and Cancer Study

		
Re-ordering of study procedures; notably: Eligibility to come before consent, post-test to come before pre-screening for trials/studies questions
 

-Most survey questions programmed as mandatory response

- Updated online arm descriptions to specify use of Qualtrics for survey administration where before had indicated Qualtrics or RedCap

- Updates to data collection and storage procedures (including collection of contact information within the survey, not separate, to facilitate referrals to studies/trials)

-Updated electronic gift card information to indicate that unclaimed gift cards may be deactivated after 6 months

-Updated data management

-Updated privacy (team member access to data)

 
Other revised documents for review:
 

-Revised Studies Referral Tracker

-Revised Pre-Screening Questions and Information about trials/studies for referral

-Revised eligibility questions (new questions/answer options), pre- and post-test surveys (new and revised questions), and pre-screening questions/information about trials/studies for referrals (new and revised questions), revised contact and identifying information questions (now all combined as a Qualtrics PDF)

 
Adding documents for review:
 

-Website education content

-Clinical trials video

 
Please note: Experimental Arm 1 (in-person) will not commence until Dartmouth/D-HH guidance supports in-person activities, in order to minimize risk of COVID-19 transmission.
	
5	8/31/2020	Updated procedures in protocol regarding order of study procedures (consent first, screening second; re-ordering of some post-test questions versus clinical trials linkages); updated	Y

PROTOCOL TITLE: Education about Health and Cancer Study

		recruitment procedures; updated PI Documents for review:	
--	--	---	--

## PROTOCOL TITLE: Education about Health and Cancer Study

		Change of PI from [name] to [name] Update of consent forms to include new PI Update Info Sheet Experimental Arm 2 with screening language Update to recruitment language to include screening language Update of study design from Observational to Interventional Updated Qualtrics survey (reorder question sequence) Updated screening question/information form Update of educational web site link Addition of potential images for advertising/recruitment Considering addition of a setting in Qualtrics with accompanying instructions that will provide the participant with a time allocation for the intervention	
6	9/21/2020	Change in protocol file name	
7	10/15/2020	Added two Qualtrics survey questions pertaining to participant's level of engagement with educational content (participants are required to respond)	
8	12/8/2020	Protocol edits: -Changes and clarifications to study procedures for online study arms, resources/team members, other procedures (see tracked changes throughout); please note: some edits are simply corrections overlooked in past modifications (e.g., eligibility screening process that was changed in modification #4 above—some residual edits were needed for clarity only).  -Updated contact information form (Exp Arm 1-document; other arms- see Qualtrics survey)  -Updated survey (instructions throughout, logic/flow, question language, contact/personal information form, linkage/referral questions)  -Updated consent/information sheet for clarity (see tracked changes in enclosed document)  -Updated tracking sheet for study teams/nurses  -Updated linkage/referral questions document	Y
9	4/20/2021	Study team edits: -Adding [name] as Co-I -Removing [name] as study team member  Protocol edits:	Y

## PROTOCOL TITLE: Education about Health and Cancer Study

		

-Removing control group

-Updating experimental arm 1 procedures

-Minor other edits

 
Updated survey for experimental arm 2 (and former control group)
 

-Removing control group intervention and 'dummy' questions from the control group

-Updating contact information throughout

-Providing clarifying instructional language

-Adding two qualitative questions about the intervention

 
Providing electronic surveys (pre and post) for experimental arm 1
 
Updated consent for experimental arm 2 (and former control group):
 

-Updating contact information

 
Updated consent for experimental arm :
 

-Updating study details

-Updating compensation

-Updating contact information

	
10	7/13/2021	

-Updating contact information for research team (instructional language in surveys, consent)

-Updating participant instructions related to timeline for compensation

-Updating study procedures for identifying bot/fake survey responses

	Y
11	9/10/2021	

-Updating PI

-Updating documents (including consents) to reflect updated PI

-Updating materials related to trials/studies we will refer to, as they also are experiencing changes in their PIs

	Y
12	3/3/2022	

-Updating recruitment plans/verbiage for Experimental Arm 2

-Clarifying team members mentioned in protocol (though they've previously been updated in eIRB system)

	N
13	05/02/2022	

Name change from Norris Cotton Cancer Center to Dartmouth Cancer Center

-Addition of new employees; removing previous employees

-Updating info for new Best Practice Alert for provider access to connect patients with clinical trials education

-Updating/clarifying listserve & Front Porch Forum information for advertising purposes

	
14	02/15/2023	

-Addition new employee; remove former employee

-Addition After Visit Summary (AVS) for Epic to BPA

-Study Population Arm 2 updated to include listserves and flyers in addition to social media

	

## 1.0 Study Summary

Study Title	Education about Health and Cancer Study
Study Design	Interventional/Cohort Study Pre-/Post-/Follow-up (via surveys and research records)
Primary Objective	Aim 1: Implement and evaluate educational activities to improve knowledge of, attitudes and behavioral intentions toward, and participation in clinical trials and cancer research studies among rural residents living in NH and VT (Rural = RUCC 7-9 counties).
Secondary Objective(s)	
Aim 1a: Implement electronic portal access to educate regarding what clinical trials and cancer research are and evaluate the effect on knowledge of, attitudes and behavioral intentions toward, and actual enrollment into clinical trials and cancer research studies.
 
Aim 1b: Implement online education regarding what clinical trials and cancer research are and evaluate the effect on knowledge of, attitudes and behavioral intentions toward, and actual enrollment into clinical trials and cancer research studies.
 
Aim 1c: Compare the impact of education about clinical trials with the impact of an innovative outreach modality using social media and web-based technology for educating the public about clinical trials; provider portal Epic (EDH) for patients.

Research Intervention(s)	
Experimental arm 1 (Aim 1a): Education about clinical trials and cancer research via provider portal education to cancer survivors, caregivers, and the public.
 
Experimental arm 2 (Aim 1b): Education about clinical trials and cancer research via online video and module.

Study Population	The main target population is adults aged 18 or older who reside in rural New Hampshire or Vermont; “rural” = Rural Urban Continuum Codes (RUCC) 7—9 counties (Coos and Sullivan County, NH; Caledonia, Windsor, Windham, Orange, Orleans, Lamoille, and Essex County, VT)

PROTOCOL TITLE: Education about Health and Cancer Study

	
To be eligible to enroll in experimental arm 1, people must be 18 years or older at the time of enrollment.
 
To be eligible to enroll in experimental arm 2, people must meet the following eligibility criteria:
 
 
-Be a resident of one of the RUCC 7—9 counties in NH and VT and
 
-Be 18 years or older at the time of enrollment
 
 
Aim 1: The target population is adult cancer survivors, caregivers, and patients who are connected with the Dartmouth Cancer Center.
 
Aim 2: The target population is adults who reside in rural New Hampshire or Vermont.

Sample Size	
Experimental Arm 1: up to 50
 
Experimental Arm 2: 200-250

Study Duration for individual participants	Up to 7.5 months
Study Specific Abbreviations/ Definitions	
BPA=Brief Provider Alerts      CHE= Community Health Educator      NCI= National Cancer Institute      CRCHD=Center to Reduce Cancer Health Disparities (a division of the National Cancer Institute)      NON= National Outreach Network (an effort of CRCHD)      COE= Community Outreach and Education (a focus of the Norris Cotton Cancer Center)      DCC=Dartmouth Cancer Center      DHH=Dartmouth Hitchcock Health      NCCC= Norris Cotton Cancer Center      NCCC North= Norris Cotton Cancer Center North in St. Johnsbury      RUCC= Rural-Urban Continuum Codes (a U.S. Department of Agriculture schema for defining communities as rural/urban)

PROTOCOL TITLE: Education about Health and Cancer Study

## **2.0 Objectives\***

**2.1** The purpose of this project is to: (1) contribute to a nation-wide initiative to educate the public about clinical trials, (2) evaluate the effectiveness of education about clinical trials/research in changing knowledge, behavioral intentions, and behaviors related to clinical trials/cancer research enrollment.

Aim 1: Implement and evaluate educational activities to improve knowledge of, attitudes and behavioral intentions toward, and participation in clinical trials and cancer research studies among rural residents living in NH and VT (Rural = RUCC 7-9 counties).

Aim 1a: Implement electronic portal education regarding what clinical trials and cancer research are and evaluate the effect on knowledge of, attitudes and behavioral intentions toward, and actual enrollment into clinical trials and cancer research studies.

Aim 1b: Implement online education regarding what clinical trials and cancer research are and evaluate the effect on knowledge of, attitudes and behavioral intentions toward, and actual enrollment into clinical trials and cancer research studies.

Aim 1c: Compare the impact of electronic education about clinical trials with the impact of an innovative outreach modality using social media, patient portals and web-based technology for educating the public about clinical trials.

## **2.2 Hypotheses:**

- 1- Assessing education about clinical trials will be effective in: a) increasing knowledge of clinical trials; b) increasing intent to participate in clinical trials; and c) increasing clinical trials/research project enrollment within six-months post-outreach.
  
- 2- Online/video outreach with online module about clinical trials will be effective in: a) increasing knowledge of clinical trials; b) increasing intent to participate in clinical trials; and c) increasing clinical trials/research project enrollment within six-months post-outreach.

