**3.3.** In order to implement education about clinical trials across 24 cancer centers, NCI/CRCHD has developed a set of key messages that all cancer centers must include in their educational activities, and the cancer centers are tailoring the educational messaging/curriculum and delivery of activities to be locally-relevant and tailored to the needs of our catchment area. NCI/CRCHD has also developed a pre-test and a post-test (surveys- see attached) that will be administered immediately preceding and proceeding our educational activities, with the intent of evaluating whether the educational interventions changed the participants' knowledge of, attitudes toward, and behavioral intentions regarding taking part in clinical trials and research. NCI/CRCHD has asked us to track whether participants in our interventions go on to enroll in trials/studies in the six-months following our intervention (via our PIs' and Office of Clinical Trials' research records).

PROTOCOL TITLE: Education about Health and Cancer Study

This study will help measure and evaluate the effectiveness of different models of educating people about clinical trials. The data will be aggregated at a national level to assess the overall NCI/CRCHD activity. The data will be analyzed at the local/regional level to inform DCC's Community Outreach and Engagement program's future outreach models. Given the limited literature regarding the effectiveness of education on clinical trials knowledge, attitudes, and enrollment, this study will contribute meaningful and important information.

References:

- 1 *Ford, J. G., Howerton, M. W., Lai, G. Y., Gary, T. L., Bolen, S., Gibbons, M. C., ... & Powe, N. R. (2008). Barriers to recruiting underrepresented populations to cancer clinical trials: a systematic review. Cancer: Interdisciplinary International Journal of the American Cancer Society, 112(2), 228-242.*
2. *Taylor, H., & Leitman, R. Misconceptions and lack of awareness greatly reduce recruitment for cancer clinical trials.[article online, Health Care News, Vol. 1, Issue 3]. Rochester (NY): Harris Interactive, Inc.; 2001 Jan 22 [cited 2001 Mar 29]. [3 p].*

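### Hypotheses 1c and 2c claim that each arm increases trial and research enrollment, but the planned data can only describe enrollment afterwards

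*Protocol*

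**What the plan says.** **The claim.** Hypotheses 1c and 2c in section 2.2 use the same words: each arm will be effective in "increasing clinical trials/research project enrollment within six-months post-outreach". Aim 1, the stated primary objective, is to improve participation, among other outcomes. Aims 1a and 1b (sections 1.0 and 2.1) are to "evaluate the effect on knowledge of, attitudes and behavioral intentions toward, and actual enrollment into clinical trials and cancer research studies". Purpose (2) in section 2.1 is to "evaluate the effectiveness of education about clinical trials/research in changing knowledge, behavioral intentions, and behaviors" related to enrollment. Section 17.1 plans tests of whether behavior, among other outcomes, changed because of the arms, and a look across groups. Aim 1c is to "Compare the impact of electronic education about clinical trials with the impact of an innovative outreach modality".

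**The data.** Section 4.2 defines the endpoint from records over the six months after the intervention. Section 6 (Arm 1 step h, Arm 2 step w) asks record holders who has enrolled since the education. Section 14.2 drops non-completers from enrollment follow-up in both arms. The end of section 6 discontinues the control arm. Arm 1 step h adds that aggregate enrollment at the cancer center will be collected for comparison; Arm 2 step w has no such sentence.

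**The people.** Section 1.0 describes Arm 1 as education "via provider portal education to cancer survivors, caregivers, and the public", and elsewhere says: "The target population is adult cancer survivors, caregivers, and patients who are connected with the Dartmouth Cancer Center". Section 10.2 limits Arm 1 only by age. Arm 2 takes adult residents of the listed rural counties, reached through social media, listserves and flyers.

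**Referral.** In both arms, participants who pre-screen as possibly eligible are connected to study teams or clinical staff, if they give permission (sections 6, 16 and 19).

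**The concern.** To say that something increased, one needs the level it would otherwise have had. The protocol states a directional hypothesis about enrollment but collects only a count after the event, in a selected group, and it has stopped its control arm. An analysis plan can choose a test, but it cannot supply a reference rate from data that the protocol does not plan to collect. This is therefore a mismatch between the hypothesis and the data, and not a detail left to later.

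The consequence lies in how the results will be used. Section 3.3 calls the literature limited on "the effectiveness of education on clinical trials knowledge, attitudes, and enrollment" and presents this study as a contribution to it. It also says: "The data will be analyzed at the local/regional level to inform" future outreach models. A six-month count reported as an increase would carry an unsupported conclusion into both.

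**Working it through.** **1. Who is followed.** Section 12 expects up to 900 consenters with about one third completing: 900 × 1/3 = 300. The completer targets are 50 + 200 = 250 to 50 + 250 = 300, so the protocol's figure matches the upper end. The other 900 − 300 = 600 mix ineligible people with eligible people who stop, in a proportion not given. The followed share of eligible consenters therefore lies between 300/900 = 33% and 300/300 = 100%.

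**2. Could anything in the protocol serve as the reference rate?**

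- *Participants' own earlier enrollment:* not collected (sections 4.2 and 6).
- *Control arm:* discontinued. Section 6 and section 17.3 withhold control data from the funder, which leaves open that some exist locally, but no use of them for enrollment is stated.
- *Aggregate cancer center enrollment:* Arm 1 only. The protocol gives it no denominator, period or matching. Arm 1 may include caregivers and others limited only by age, and those followed are self-selected completers.
- *The other arm:* both arms receive education and pre-screening, with referral where applicable, and they draw on different populations. A difference between them does not show that either arm raised enrollment.

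Arm 2, and so hypothesis 2c, has no outside comparator at all.

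**3. What a count leaves open.** Increase = observed rate − rate without the intervention. The second term is not collected, and the protocol gives no enrollment rate, so these rates are assumptions.

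- Observed 5/250 = 1/50 = 2%. If the missing rate is 0, 1, 2 or 4%, the increase is +2, +1, 0 or −2 points.
- Observed 25/250 = 5/50 = 10%. If the missing rate is 0, 10 or 20%, the increase is +10, 0 or −10 points.

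**4. The completer restriction alone.** Suppose the intervention has no effect, one third complete, and completers would enroll at R times the rate of non-completers. The completer rate divided by the rate in all consenters is R / (R/3 + 2/3).

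- R = 2: 2 / (4/3) = 1.5
- R = 4: 4 / 2 = 2.0
- R = 0.5: 0.5 / (2.5/3) = 0.6

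R is an assumption. These are the extreme values for each R, reached if all 600 others were eligible. The ratio moves towards 1 as more of them are ineligible.

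**5. Referral.** Some participants are handed to study teams whose enrollments are then counted. Any observed enrollment therefore belongs to education plus pre-screening plus, where it happened, referral. This applies equally to hypotheses 1c and 2c: both refer to outreach, and both arms list these steps among their procedures.

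**6. What the data can give.** Exact 95% intervals for a described proportion, with assumed counts:

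- 1/50: 0.1 to 10.6%
- 5/50: 3.3 to 21.8%
- 5/250: 0.7 to 4.6%
- 25/250: 6.6 to 14.4%

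**The case against.** The best defense is that comparisons are planned. Arm 1 step h names aggregate cancer center enrollment, section 17.1 looks across groups, and an analysis plan not seen here may define both. Arm 1 is also closer to that aggregate than the mention of the public suggests: the population statement names people connected with the center, and section 13 recruits through an alert to cancer providers at the point of care. This stands in part. A reader might infer that no comparison is planned, and that would be wrong. But the aggregate remains unlike the followed group, and it is not offered for Arm 2.

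Control data may exist, and section 24 recruits that arm alongside Arm 2, so it would be the nearest comparator for 2c. Whether it will be used cannot be settled from this document, which states no such use. A look-back in the same records is also conceivable, since identifiers are collected. The protocol does not plan one, and a before-and-after count would have biases of its own.

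It is fair to say that the illustrations in steps 3 and 4 would apply to any uncontrolled count. They show only that the sign is open. They do not estimate a bias in this trial.

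Finally, the design is openly labelled a pre/post/follow-up cohort, a hypothesis is not a result, and the funder asked only for tracking. This limits the severity, but it does not make the stated hypothesis testable.

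**Conclusion.** The point holds. Hypotheses 1c and 2c, the participation or enrollment parts of Aims 1, 1a and 1b, purpose (2) and the behavior part of section 17.1 state an effect that the planned data cannot show. The conclusion rests on the protocol's own follow-up window, completer rule and removal of the control arm. It needs no assumed rate. It should be corrected, but it does not undermine the study as a whole.

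Three stronger readings are not supported:

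- A reader might infer that the count will overstate the effect. With no enrollment rate and no reference, neither the size nor the sign of the bias is known.
- A reader might infer that referral, and not education, will produce the enrollments. Only possibly eligible and willing participants are referred; the documents show that the parts cannot be separated, not which part works.
- A reader might extend the point to knowledge, attitudes and intentions. Those have a pre-test and are outside it.

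**What to change.** 1. Delete item c from hypotheses 1 and 2 in section 2.2, and add a separate descriptive objective: *For each arm we will report the proportion of participants completing all study procedures who are recorded as enrolled in a DCC trial or research study within six months after the educational intervention, with an exact 95% confidence interval.*
2. Align Aims 1, 1a, 1b and 1c (sections 1.0 and 2.1), purpose (2) and the behavior part of section 17.1. State that no increase in enrollment due to the intervention is claimed, and that the between-arm difference in enrollment has no causal reading.
3. Use aggregate cancer center enrollment as context only. For this outcome, describe the intervention as education with pre-screening and, where applicable, referral.

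The cost is a weaker stated claim and an IRB modification for the wording, which should say openly why the hypotheses changed. No new data are collected, the sample size is unchanged, and the funder's tracking request in section 3.3 is still met.
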